5.7.2 Handling of Participant Withdrawals or Termination

Discontinuation of the study agent is not anticipated as this will place patients at risk to develop acute or chronic HCV. For patients who do elect to discontinue the study agent Mavyret due to intolerance or SAEs/AEs, the following steps will be taken:

Hepatology consultation to guide management, which could include:

Continued surveillance for evidence of HCV viremia in patients who had cleared their viremia
Conversion to an alternate HCV treatment that is able to be tolerated by the patient

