7.3.3 Intermediate Visits

For the schedules below, the following time-post-event designations will be used:

POW (Post-operative week) – refers to weeks following the transplant operation

PMW (Post-Mavyret treatment week) – refers to weeks following the initiation of Mavyret therapy

All patients post-transplant will enter the Surveillance Phase which will entail weekly screening for the development of HCV viremia post-transplant for 8 weeks. Time in the surveillance phase is measured in reference to the transplant itself, in POW. Patients who never develop HCV viremia during the Surveillance Phase will transition to the No Transmission schedule detailed below. Time in the No Transmission arm is measured in reference to the transplant itself, in POW.

Patients who develop detectable HCV viremia during the Surveillance Phase will immediately exit the Surveillance Phase and enter the Mavyret Treatment arm schedule as detailed below. Time in the Mayvret Treatment arm is measured in reference to the date that Mavyret treatment was initiated, in PMW.

SURVEILLANCE PHASE SCHEDULE OF EVENTS

POW1 (+/- 1 day)

- In person visit, record vital signs
- Record standard of care labs: hematology, biochemistry, coagulation
- Collect study labs: HCV NAT

POW2 (+/- 2 days)

- In person visit, record vital signs
- Record standard of care labs: hematology, biochemistry, coagulation
- Collect study labs: HCV NAT

POW3 (+/- 3 days)

- Record standard of care labs: hematology, biochemistry, coagulation
- Collect study labs: HCV NAT

POW4 (+/- 5 days)

- In person visit, record vital signs
- Record standard of care labs: hematology, biochemistry, coagulation, HBV serologies and NAT, HIV serologies
- Collect study labs: HCV NAT

CONFIDENTIAL

This material is the property of the NYU School of Medicine and Langone Medical Center. Do not disclose or use except as authorized in writing by the study sponsor

POW5 (+/- 5 days)

- Record standard of care labs: hematology, biochemistry, coagulation
- Collect study labs: HCV NAT

POW6 (+/- 5 days)

- Record standard of care labs: hematology, biochemistry, coagulation
- Collect study labs: HCV NAT

POW7 (+/- 5 days)

- Record standard of care labs: hematology, biochemistry, coagulation
- Collect study labs: HCV NAT

POW8 (+/- 5 days)

- Record vital signs
- Record standard of care labs: hematology, biochemistry, coagulation,
- Collect study labs: HCV NAT and serology

NO TRANSMISSION ARM SCHEDULE OF EVENTS

POW12 (+/- 7 days)

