8.5 Study Halting Rules

Further enrollment of study subjects will be halted under the following conditions:

- Any patient death occurs and is deemed related to the intervention
- Any SAE deemed related to acute HCV infection occurs
- Any SAE deemed related to Mavyret occurs

The PI will inform the IRB and the DSMB within 24 hours of any of these events. The DSMB and study team will convene an emergency meeting as described below. The DSMB will provide recommendations for proceeding with any further enrollment. Patients who are already enrolled and receiving Mavyret treatment will continue to receive treatment unless the DSMB determines that an alternate course of therapy should be pursued for already-enrolled subjects.

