10.4.7.1 Safety Review

Any patient death will result in halting of any further enrollment in the study and an assessment of whether the death was related to HCV exposure, infection, or treatment. Even in the event of a patient death, currently enrolled patients who are actively being treated for HCV viremia and tolerating therapy will continue to receive therapy so as not to put them at risk for HCV infection and/or the development of resistance as a consequence of interrupted therapy. If the patient death is deemed related to a specific treatment agent, enrolled patients receiving that same agent will be switched to an alternative therapy.

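### After a death attributed to Mavyret, Protocol sections 8.5 and 10.4.7.1 give opposite instructions for patients already on the drug, and neither sets a default for recipients not yet viremic

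*Protocol*

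**What the plan says.** Protocol section 8.5 halts further enrollment on any of three events: "Any patient death occurs and is deemed related to the intervention", "Any SAE deemed related to acute HCV infection occurs" or "Any SAE deemed related to Mavyret occurs". For patients on treatment at that time it says "Patients who are already enrolled and receiving Mavyret treatment will continue to receive treatment unless the DSMB determines" that a different course should be pursued for subjects already enrolled. The IRB and the DSMB are to be told within 24 hours, and an emergency meeting follows.

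Section 10.4.7.1 deals only with deaths. After any death, patients who are on treatment and tolerating it continue. It then makes an exception for a death attributed to a particular agent, in which case "enrolled patients receiving that same agent will be switched to an alternative therapy". This sentence is unconditional, mentions no DSMB decision and does not refer to section 8.5.

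Section 7.3.3 governs recipients who are transplanted but not yet treated: "Patients who develop detectable HCV viremia during the Surveillance Phase will immediately exit the Surveillance Phase and enter the Mavyret Treatment arm schedule". It makes no exception for an enrollment halt or for an agent-related death.

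**The concern.** The texts are emergency instructions for the gravest event the trial could produce. For a death attributed to Mavyret, one section keeps the other treated patients on the drug until the DSMB says otherwise. The other takes them off it without naming anyone who decides.

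A recipient already transplanted and still under surveillance cannot be un-enrolled in any useful sense, because the exposure has already happened. If that recipient becomes viremic before the DSMB has ruled, section 7.3.3 starts Mavyret while section 10.4.7.1 is moving current patients off it.

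There is also a counting question. The hypothesis (Protocol 10.2, SAP 1.2) concerns SVR after a completed 8-week Mavyret course. The primary endpoint (Protocol 4.2.1 and 10.4.2, SAP 1.4.2) concerns SVR after HCV treatment and names no agent. A patient switched by rule in mid-course can fit the endpoint but not the hypothesis, and neither document says how that patient is counted.

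**Working it through.** No stated figure is at issue, so the check sets the rules side by side, event by event.

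A Mavyret-related death falls under section 8.5 by two routes. The Protocol Summary lists treatment of viremia among the study-specific interventions, so the death is related to the intervention. Section 8.1.2 also counts a fatal event as an SAE, so it is a Mavyret-related SAE as well.

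| Event | Section 8.5 | Section 10.4.7.1 | Result |
|---|---|---|---|
| Death related to Mavyret | Continue unless the DSMB decides otherwise | Switch; no DSMB step named | Conflict |
| Death related to the intervention but not to the agent | Continue unless the DSMB decides otherwise | Continue if tolerating | Same default |
| Non-fatal SAE related to Mavyret | Continue unless the DSMB decides otherwise | Silent | One rule |
| Non-fatal SAE related to acute HCV | Continue unless the DSMB decides otherwise | Silent | One rule |

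For transplanted, untreated recipients:
- The halt in 8.5 stops new enrollment only, and its default sentence names patients receiving Mavyret.
- 10.4.7.1 names patients being treated or receiving the agent.
- 7.3.3 continues to apply, with Mavyret starting at PMW0, within 5 days of viremia being determined.
- No explicit interim default exists for this group.

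**Scale, for orientation only.** Inputs from the Protocol: N of 10 (10.5) or 20 (5.6), about 70% becoming viremic (10.5), 8 weeks of treatment (6.1.8) and 8 weeks of surveillance (7.3.3). Expected treated: 10 × 0.70 = 7, which reproduces the figure in 10.5; 20 × 0.70 = 14. Assumptions, not in the documents: even accrual over A = 52 to 104 weeks, and viremia found t = 1 to 8 weeks after transplant.

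- Mean number on Mavyret = (N/A) × 0.70 × 8. For N = 10: 0.54 (A = 104) to 1.08 (A = 52). For N = 20: 1.08 to 2.15.
- Mean number in surveillance and untreated = (N/A) × (0.30 × 8 + 0.70 × t). For N = 10: 10/104 × 3.1 = 0.30 to 10/52 × 8 = 1.54. For N = 20: 0.60 to 3.08.
- Chance that both groups are present at a given moment, treating the two counts as independent Poisson variables = (1 − e^−on) × (1 − e^−surv), where on and surv are the two means above. For N = 10: 11% to 52%. For N = 20: 30% to 84%.

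**The case against.** The strongest reply is that oversight would resolve the matter quickly. Every event in section 8.5 requires notice within 24 hours. Section 8.6 sets emergency meetings within one business day, with the principal investigator present, and this is a single-center study. The switch in 10.4.7.1 could be read as what the DSMB would order under its 8.5 power. The DSMB charter is a separate attachment, not available here, and may say who decides. This makes a prolonged split unlikely. It does not remove the conflict: 10.4.7.1 is unconditional and names no DSMB step, and section 8.6 sets a deadline for the meeting but not for the ruling.

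Four stronger readings are tempting, and the documents do not support them.

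- A reader might infer that the sections also conflict after a non-fatal SAE. They do not, because every rule in 10.4.7.1, including its tolerance qualifier, depends on a death.
- A reader might infer that section 5.7.2, which allows "Conversion to an alternate HCV treatment that is able to be tolerated by the patient", contradicts 8.5. It governs a patient who chooses to stop. The default for treated patients after a halting event does not override that choice.
- A reader might infer that nothing in the plan reaches recipients in surveillance. The 8.5 sentence ends by referring to subjects already enrolled, and these recipients consented before transplant (7.3.2). The DSMB's power can be read to include them, so what is missing is only a default until it is used.
- A reader might infer that each switched patient is lost from the primary result, at 1/14 to 1/7 (about 7 to 14 percentage points) apiece. The endpoint names no agent, so such a patient is not clearly removed. Section 10.4.4 defines failure as viremia persisting after the full course, so a directed mid-course switch is not clearly a failure either.

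**Conclusion.** The point stands in a narrow form. For a death deemed related to Mavyret, sections 8.5 and 10.4.7.1 conflict on both the default action for other treated patients and the authority to change it. For transplanted recipients not yet viremic there is no explicit interim default, and section 7.3.3 would start Mavyret on viremia until the DSMB acts.

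Both findings come from the text and need no numerical assumption. The scale is small: about 0.5 to 2.2 patients on drug and 0.3 to 3.1 in untreated surveillance at any moment, under the assumed accrual and timing. The documents give no probability for a Mavyret-related death, so no expected harm can be calculated. The case for acting is that these are safety instructions for an emergency and the repair is cheap. Which clinical rule is right is not judged here.

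**What to change.** Reconcile sections 8.5 and 10.4.7.1 into one rule, cross-referenced between them and from 7.3.3. It should name who decides and state what applies to:

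- (a) patients on Mavyret when the event occurs;
- (b) transplanted recipients who become viremic before the DSMB has ruled.

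The investigators and the DSMB should settle the clinical content.

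Record any rule-directed switch with its date, agent and reason. State in Protocol 10.4.2 and SAP 1.4.2 how such a patient is counted for the primary endpoint, and in Protocol 10.2 and SAP 1.2 how that patient is counted for the hypothesis of SVR after 8 weeks of Mavyret.

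The cost is a text amendment and a check against the DSMB charter. No patients, visits or tests are added.

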10.4.8 Multiple Comparison/Multiplicity

Not applicable.

10.4.9 Tabulation of Individual Response Data

Since this is a relatively small trial, individual participant data, in particular as pertains to the kinetics of the development and clearance of HCV viremia, will be evaluated.

CONFIDENTIAL

This material is the property of the NYU School of Medicine and Langone Medical Center. Do not disclose or use except as authorized in writing by the study sponsor

Interventional Template Version: 28 APR 2017

10.5 Sample Size

10 patients are expected to enroll in this trial.

We expect that less approximately 70% of patients will develop evidence of HCV infection transmitted from the HCV-positive donor and will be treated for HCV infection. We expect that 100% of the patients who are treated for HCV infection will achieve SVR.

This is a single-arm study with no comparison group. The power to detect a difference in observed versus expected depends upon the true efficacy of the therapy. The reported efficacy of the therapy is 98%. With an estimated 7 patients who will be treated, a single treatment failure will be regarded as a significant deviation from the expected outcome.

11 Source Documents and Access to Source Data/Documents

Source data is all information, original records of clinical findings, observations, or other activities in a clinical trial necessary for the reconstruction and evaluation of the trial. Source data are contained in source documents. Examples of these original documents, and data records include: hospital records, clinical and office charts, laboratory notes, memoranda, subjects' diaries or evaluation checklists, pharmacy dispensing records, recorded data from automated instruments, copies or transcriptions certified after verification as being accurate and complete, microfiches, photographic negatives, microfilm or magnetic media, x-rays, subject files, and records kept at the pharmacy, at the laboratories, and at medico-technical departments involved in the clinical trial. It is acceptable to use CRFs as source documents. If this is the case, it should be stated in this section what data will be collected on CRFs and what data will be collected from other sources.

The study case report form (CRF) is the primary data collection instrument for the study. All data requested on the CRF must be recorded. All missing data must be explained. If a space on the CRF is left blank because the procedure was not done or the question was not asked, write "N/D". If the item is not applicable to the individual case, write "N/A". All entries should be printed legibly in black ink. If any entry error has been made, to correct such an error, draw a single straight line through the incorrect entry and enter the correct data above it. All such changes must be initialed and dated. DO NOT ERASE OR WHITE OUT ERRORS. For clarification of illegible or uncertain entries, print the clarification above the item, then initial and date it.

Access to study records will be limited to IRB-approved members of the study team. The investigator will permit study-related monitoring, audits, and inspections by the IRB/EC, the sponsor, government regulatory bodies, and University compliance and quality assurance groups of all study related documents (e.g. source documents, regulatory documents, data collection instruments, study data etc.). The investigator will ensure the capability for inspections of applicable study-related facilities (e.g. pharmacy, diagnostic laboratory, etc.).

Participation as an investigator in this study implies acceptance of potential inspection by government regulatory authorities and applicable University compliance and quality assurance offices.

12 Quality Assurance and Quality Control

QC procedures will be implemented beginning with the data entry system and data QC checks that will be run on the database will be generated. Any missing data or data anomalies will be communicated to the site(s) for clarification/resolution.

Following written SOPs, the monitors will verify that the clinical trial is conducted and data are generated, documented (recorded), and reported in compliance with the protocol, GCP, and the applicable regulatory requirements (e.g., Good Laboratory Practices (GLP), Good Manufacturing Practices (GMP)).

CONFIDENTIAL

This material is the property of the NYU School of Medicine and Langone Medical Center. Do not disclose or use except as authorized in writing by the study sponsor
Interventional Template Version: 28 APR 2017

The investigational site will provide direct access to all trial related sites, source data/documents, and reports for the purpose of monitoring and auditing by the sponsor, and inspection by local and regulatory authorities.

13 Ethics/Protection of Human Subjects

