In this pilot study we propose utilizing HCV positive donors for HCV negative patients on the waiting list for a heart transplant at NYU Langone. We will propose careful early post-transplant surveillance for the development of HCV viremia. We anticipate that approximately one-third of the patients will not develop viremia, despite the donor designation HCV positive. We anticipate that two-thirds of patients will develop early post-transplant HCV viremia. These patients will be immediately treated with an FDA-approved anti-HCV therapy which we expect will cure the HCV.

Willingness to participate in this trial will afford patients quicker access to heart transplantation, and will have the potential to reduce waitlist mortality.

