5.4 Strategies for Recruitment and Retention

Recruitment of patients will occur during routine evaluation visits to determine candidacy for a heart transplant at NYU Langone Health. Patients will be informed of the option to enroll in this study, and if interested, detailed information pertaining to the risks and benefits of the trial will be provided.

The signing of the acknowledgment to consider participation in the study will occur in the outpatient clinic. No additional information about potential candidates will be collected to determine interest or candidacy for this trial than would otherwise be normally collected as per standard of care for evaluation for a heart transplant.

Written informed consent for actual enrollment in the study will occur in the inpatient setting once a viable organ offer has been identified and the patient is admitted for potential transplantation.

The target sample size will be 20 patients.

CONFIDENTIAL

This material is the property of the NYU School of Medicine and Langone Medical Center. Do not disclose or use except as authorized in writing by the study sponsor
Interventional Template Version: 28 APR 2017

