5.6 Total Number of Participants and Sites

20 patients are expected to be enrolled and transplanted. No sites outside of NYULMC will enroll patients.

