13.2 Institutional Review Board

The protocol, informed consent form, recruitment materials, and all participant materials will be submitted to the IRB for review and approval. Approval of both the protocol and the consent form must be obtained before any participant is enrolled. Any amendment to the protocol will require review and approval by the IRB before the changes are implemented to the study. All changes to the consent form will be IRB approved; a determination will be made regarding whether previously consented participants need to be re-consented.

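### The protocol plans for 10 patients in two places and 20 in two others, so the number of HCV-negative recipients to be exposed is uncertain by a factor of two

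*Protocol*

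**What the plan says.** Four places in the protocol give the planned number of patients, and they split two against two.

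- **Protocol Summary, number of participants:** ten.
- **Section 10.5, Sample Size:** "10 patients are expected to enroll in this trial".
- **Section 5.4, Strategies for Recruitment and Retention:** "The target sample size will be 20 patients".
- **Section 5.6, Total Number of Participants and Sites:** "20 patients are expected to be enrolled and transplanted".

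Section 10.5 then derives one further figure. It gives the transmission rate as "We expect that less approximately 70% of patients will develop evidence of HCV infection transmitted from the HCV-positive donor" and goes on "With an estimated 7 patients who will be treated". Section 2.1 puts the rate slightly differently: "We anticipate that two-thirds of patients will develop early post-transplant HCV viremia".

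The SAP text available for review states no sample size. Part of the SAP was not available, so nothing is inferred from that silence.

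**The concern.** These are the sections a reader would consult for the planned size of the study. A reader of the Summary or 10.5 concludes that ten HCV-negative people will be exposed to a donor heart that may carry HCV. A reader of 5.4 or 5.6 concludes that twenty will be. Section 2.4.1 sets out what exposure can involve: treatment failure, acute infection with rare fulminant hepatic failure, and chronic infection.

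The practical difficulty comes with the eleventh transplant. Under 5.4 and 5.6 it is planned accrual; under the Summary and 10.5 it goes beyond the plan. From the protocol text alone, neither the IRB nor the DSMB can tell which applies.

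The primary endpoint is the percentage of treated patients who reach sustained virologic response (SVR), so its expected denominator is uncertain by the same factor.

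**Working it through.** **1. Can both totals be true?** Three readings were tried.

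- *Expected number against target number.* This fails. Sections 5.6 and 10.5 both describe an expected number, and they give 20 and 10.
- *Consented against transplanted.* This fails on 5.6, where the 20 are both enrolled and transplanted, while the 10 in section 10.5 are those who enroll. Those transplanted in the study cannot outnumber those enrolled. The consent timing in 5.4 points the same way: "Written informed consent for actual enrollment in the study will occur in the inpatient setting once a viable organ offer has been identified". The earlier written acknowledgement at screening (section 7.3.1) is a separate step and is not enrollment.
- *Transplanted against treated.* This fails because 10.5 gives the number treated separately, as 7.

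**2. Which total does the 7 in section 10.5 come from?** Inputs are the total N (10 or 20) and the transmission rate (70% in 10.5, two-thirds in 2.1). The formula is expected treated = N × rate.

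| N | rate 70% | rate two-thirds |
|---|---|---|
| 10 | 10 × 0.70 = 7.0 | 10 × 2/3 = 6.7 |
| 20 | 20 × 0.70 = 14.0 | 20 × 2/3 = 13.3 |

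The protocol's 7 is reproduced from N = 10 at either rate, after rounding, and from N = 20 at neither. The 14 is inferred here; the protocol does not state it. Section 10.5 is consistent within itself, and the conflict is between sections.

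**3. Can either total be derived?** No. The protocol gives no power, precision target, margin or dropout allowance from which N could be calculated, so arithmetic cannot show which figure was intended.

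**4. What the difference means for the primary endpoint (illustration only).** If every treated patient is cured, the exact two-sided 95% lower limit for SVR is 0.025^(1/n), where n is the number treated:

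- n = 7: 0.025^(1/7) = 59.0%
- n = 14: 0.025^(1/14) = 76.8%

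**The case against.** The strongest case on the other side concerns weight. The analysis is mainly descriptive and no stated power or precision is lost. The endpoint definitions (10.4.2, 10.4.3), the halting rules (8.5, 10.4.7.1), the DSMB meeting triggers (8.6) and the handling of treatment failures (10.4.4) do not use N. Halting follows from single events, so those protections work the same at 10 or 20. All of that stands, and it limits the consequences to the planned number exposed and the expected denominator.

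Four narrower points also deserve to be granted:

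- The wording is of expected and target numbers, and no maximum is stated. These are two conflicting plans, not two conflicting caps.
- The consent form, the Fact Sheet, the DSMB Charter and the study schematic were not available and may state a number. They could show what was intended, but they would not remove the conflict from the protocol.
- Consent after an organ offer does not by itself exclude a patient who consents and is then not transplanted. Section 5.6 carries that argument.
- The 70% sentence in 10.5 is garbled. If it meant less than 70%, then 7 and 14 are upper figures. The 7 would still fit a total of 10 far better than 20.

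None of these offers a reading under which both totals hold.

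**Conclusion.** The inconsistency is real and must be corrected. Planned accrual is 10 or 20. Expected treated is 7 or 14 at 70% transmission, or 6.7 or 13.3 at two-thirds. It is not a single slip of the pen: each total appears in two sections, and the 7 in 10.5 was built on the smaller one. The finding rests on the current protocol text and on the protocol's own transmission rates. It does not say which total was intended, because the documents do not settle that.

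**What to change.** State one planned number in the Protocol Summary and in sections 5.4, 5.6 and 10.5, preferably defined as recipients transplanted under the protocol. Make the expected number treated in 10.5 agree with it: 7 if the total is 10, 14 if it is 20, at 70%. Repair the garbled 70% sentence at the same time. Check that any number in the consent form, Fact Sheet, DSMB Charter and schematic agrees.

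If 10 is intended, sections 5.4 and 5.6 change. If 20 is intended, the Summary and 10.5 change, including the 7. Section 13.2 sets the route: "Any amendment to the protocol will require review and approval by the IRB before the changes are implemented to the study". The cost is wording and one IRB submission, with no new visits, data or patients.

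Choosing the total does not settle the separate statement in 10.5 that one treatment failure would count as a significant departure from expectation. At 98% efficacy, the chance of at least one failure is 1 − 0.98^7 = 13.2% with 7 treated and 1 − 0.98^14 = 24.6% with 14. That sentence needs its own review whichever number is chosen.
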